### **5.9.5. Analysis of Vital Signs**

Vital signs (temperature, pulse, blood pressure, orthostatic blood pressure/heart rate, and respiration rate) will be summarized by baseline and change from baseline to each scheduled assessment time with descriptive statistics by treatment group and combined fasinumab for the SAF.

PCSV summary including orthostatic hypotension will be summarized.

### **5.9.6. Analysis of 12-Lead ECG**

ECG parameters (Ventricular Rate, PR Interval, QRS Interval, QT Interval, RR Interval, QTcF QTcB interval) will be summarized by baseline and change from baseline to each scheduled

assessment time. PCSV summary of ECG parameters will be provided for on-treatment period, follow-up period, and overall for the SAF.

ECG status (i.e. normal, abnormal) will be reported. Shift tables will be provided to present the post-baseline status according to the baseline status (normal or missing / abnormal) by treatment.

#### **5.9.7. Physical Exams**

The number and percentage of patients with new-onset abnormal physical examinations will be summarized by body system by visit based on the SAF.

#### **5.9.8. Joint Pain Questionnaire**

The number and percentage of patients with significantly worse joint pain will be summarized by visit and joint based on the SAF.

#### **5.9.9. Arthropathy Adjudications**

The number and percentage of patients with images requiring arthropathy adjudication as well as the number and percentage of those patients with confirmed adjudicated arthropathy will be summarized based on the SAF. Subtypes of AAs and outcomes of AAs will also be summarized. Patient listings of cases confirmed by adjudication will be provided.

#### **5.9.10. Neurological Exam**

The number and percentage of patients with new-onset abnormal neurological examinations will be summarized by Neurological evaluations by visit based on the SAF.

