8.2.3.6. Neurologic Examination

A full or a brief neurological examination will be performed at the time points indicated in [Table 1](#). Neurological findings at baseline that are not exclusionary should be recorded in the medical history. Findings at subsequent visits will be assessed by the investigator to determine if these should be recorded as an AE.

The neurological examination will cover the following domains: motor, sensory, cranial nerves, reflexes, and coordination/balance, and assessment for presence/absence of signs of carpal tunnel syndrome. Any clinician at the site qualified to do so may conduct the neurological examination. Whenever possible, the same clinician who conducts the baseline neurological examination should continue to conduct the examinations on a given patient. The investigator may refer patients with persistent or worsening neurologic symptoms for a neurologic consultation, if clinically indicated. Additional neurologic assessments will include nerve conduction studies and other tests as deemed clinically necessary in the judgement of the neurologist.

Complete guidance on how to conduct the full and the brief neurologic examination is provided in the study reference manual.

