#### 4.5.8. Physical and Neurological Examination Variables

Physical examination assessments will be described as normal or abnormal for each body system examined. Neurological evaluations of specific domains as listed in the protocol will be described as normal or abnormal.

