### 6.1. Definition of Baseline for Variables

Unless otherwise specified, the baseline assessment for all efficacy measurements/ patient reported outcomes will be the latest available valid measurement prior to or on the day of randomization. Baseline for safety assessments such as labs, ECGs, vital signs etc. will be the latest assessment prior to the start of treatment.

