eDiary compliance 			X		X	X	X	X									
Concomitant therapies	X	X	X	X	X	X	X	X	X	X	X	X	X	X	X	X	X
Safety:																	
Weight	X								X	X					X	X	
Vital signs	X	X	X		X	X	X	X	X	X	X				X	X	
Orthostatic blood pressure and heart rate assessment 	X	X	X		X	X	X	X	X	X	X				X	X	
Electrocardiogram	X								X	X							
Physical examination	X								X	X					X	X	
Neurologic examination	X Full		X Brief		X Brief	X Brief	X Brief	X Brief	X Full	X Full	X Brief				X Full	X Full	

	Screening/ Pre-rand		Treatment Period								Follow-up Period						
Study Week	Screen	Pre-rand	Base-line	Wk 1	Wk 2	Wk 4	Wk 8	Wk 12	EOT Wk 16	ET  / JR Pre-op	Wk 20	Wk 24	Wk 28	Wk 32	Wk 36	ET  / JR Pre-op	EOS Wk 64
Study Visit/Phone	Visit 1	Visit 2	Visit 3	Phone 1	Visit 4	Visit 5	Visit 6	Visit 7	Visit 8		Visit 9	Phone 2	Phone 3	Phone 4	Visit 10		Phone 5 
Study Day (visit window)	Up to 30 days	7 to 10 days	1	8 (±1)	15 (±3)	29 (±7)	57 (±7)	85 (±7)	113 (±7)		141 (±7)	169 (±7)	197 (±7)	225 (±7)	253 (±7)		449 (±7)
Survey of autonomic symptoms	X		X		X	X	X	X	X	X	X				X	X	
Joint pain questionnaire	X		X		X	X	X	X	X	X	X				X	X	
Event-triggered imaging 				X	X	X	X	X	X	X	X				X	X	
Adverse events	----->																
SC injection site evaluation			X			X	X	X									
Bilateral X-rays (knee, hip, shoulder)	X 								X 	X 					X 	X 	
MRI (any knee with K-L ≥3 and any hip with K-L ≥2 at screening) 	X																
Pre-op questionnaire (JR) 										X						X	
EOS phone contact 																	X
MRI affected joint(s) - AA patients only 																	X
Laboratory Testing:																	
Hematology 	X					X	X	X	X	X					X	X	
Blood chemistry 	X					X	X	X	X	X					X	X	
ESR	X																
HbA1c 	X																
Urinalysis and urine electrolytes 	X								X	X					X	X	
FSH and estradiol 	X																

	Screening/ Pre-rand		Treatment Period								Follow-up Period						
Study Week	Screen	Pre-rand	Base-line	Wk 1	Wk 2	Wk 4	Wk 8	Wk 12	EOT Wk 16	ET  /JR Pre-op	Wk 20	Wk 24	Wk 28	Wk 32	Wk 36	ET  /JR Pre-op	EOS Wk 64
Study Visit/Phone	Visit 1	Visit 2	Visit 3	Phone 1	Visit 4	Visit 5	Visit 6	Visit 7	Visit 8		Visit 9	Phone 2	Phone 3	Phone 4	Visit 10		Phone 5 

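### New-onset neurological abnormalities at full-exam visits are judged against a brief Day 1 exam, and the by-visit table does not separate the two exam types

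*SAP*

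**What the plan says.** The analysis rule is one sentence in SAP 5.9.10: "The number and percentage of patients with new-onset abnormal neurological examinations will be summarized by Neurological evaluations by visit based on the SAF". SAP 4.5.8 gives the unit: "Neurological evaluations of specific domains as listed in the protocol will be described as normal or abnormal". Read together, these describe a table by domain and by visit. Neither section mentions the exam version, and new-onset is not defined for this exam.

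Protocol 8.2.3.6 provides for two versions: "A full or a brief neurological examination will be performed at the time points indicated in" the schedule table. It gives a single domain list, "The neurological examination will cover the following domains: motor, sensory, cranial nerves, reflexes, and coordination/balance", plus signs of carpal tunnel syndrome, and does not divide it between the versions. Their content is deferred: "Complete guidance on how to conduct the full and the brief neurologic examination is provided in the study reference manual".

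Protocol Table 1 and SAP Table 2 agree on the schedule:

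- Full: Screening, Week 16, Week 36 and both ET visits.
- Brief: Baseline (Day 1) and Weeks 2, 4, 8, 12 and 20.

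On baseline, SAP 6.1 says: "Baseline for safety assessments such as labs, ECGs, vital signs etc. will be the latest assessment prior to the start of treatment". SAP 4.5, which lists neurological exams among the safety data, likewise takes the last available value before the first dose.

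**The concern.** A finding is new-onset only relative to a reference exam. Here the reference for a Week 16 or Week 36 full exam is, for any domain tested on Day 1, a brief exam. A full Screening exam exists but is superseded by the later brief one. If the brief version probes a domain in less depth, a long-standing abnormality can be recorded at Screening, missed on Day 1, found again at Week 16 and tabulated as new.

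The same mismatch affects the time course. The scheduled post-baseline sequence is four brief exams, one full, one brief, one full. A higher count at Week 16 followed by a lower one at Week 20 could be read as toxicity building up on treatment and then resolving, when only the exam changed.

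Protocol 9.6.1.3 names altered peripheral sensation as an important identified risk. The protocol introduction also reports that abnormal vibration sense was more frequent on fasinumab in earlier neurological evaluations. Which exam findings count as new therefore matters, even in a descriptive table.

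**Working it through.** The plan gives no rate of neurological abnormality, so there is no figure to reproduce. The check is a reading of the rules, followed by an illustration on stated assumptions.

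**1. Count the exams.** The scheduled post-baseline exams number seven: five brief (Weeks 2, 4, 8, 12, 20) and two full (Weeks 16, 36). ET exams are also full.

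**2. Apply the baseline rule to a domain.**

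- Domain tested on Day 1: the last pre-dose value is the brief Day 1 result, and the full Screening result is not used.
- Domain not tested on Day 1: the last available value under SAP 4.5 is the full Screening result, so the comparison is already like with like.

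The problem is therefore confined to domains that both versions test but to different depths.

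**3. Follow one patient.** Screening (full) abnormal; Day 1 (brief) normal; Week 16 (full) abnormal. Baseline is normal under SAP 4.5 and 6.1, so Week 16 is new-onset although nothing changed.

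**4. Early termination.** SAP 6.4 maps ET visits by study day. A full ET exam on Day 60, for example, falls in the Week 8 window (Days 44 to 71), where the scheduled exam is brief. The two versions can thus mix within one column.

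**5. Illustrate the size.** Let q be the share of patients with a stable pre-existing abnormality in a domain that the full exam finds each time, and b the share of these that the brief exam also finds. With no true change, the share wrongly classed as new at a full visit is q × (1 − b). Both q and b are assumptions.

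| b | q = 3% | q = 10% |
|---|---|---|
| 0.5 | 1.5% | 5.0% |
| 0.7 | 0.9% | 3.0% |
| 0.9 | 0.3% | 1.0% |
| 1.0 | 0% | 0% |

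SAP 1.1 reports 63 patients randomized, or about 31 per arm (63/2 = 31.5). At q = 10% the expected number of misclassed patients per arm and domain is 31 × 0.05 = 1.55 at b = 0.5 and 31 × 0.01 = 0.31 at b = 0.9. One patient is 1/31, or about 3.2 percentage points.

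**The case against.** Several stronger readings are tempting, and the documents do not support them.

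- *Rates step up at Weeks 16 and 36 by construction.* This is not shown. Protocol 8.2.3.6 does not say what the brief exam leaves out. If it tests every domain equally well (b = 1), there is no step and no misclassification. Any fold-increase is an assumption about a manual outside the documents.
- *All findings are pooled into one series.* SAP 5.9.10 with 4.5.8 gives a table by domain. A domain not examined at a brief visit has no data there; it does not show a falsely low rate.
- *There is no denominator of patients examined.* SAP Section 6 leaves patients with missing data out of percentages unless otherwise specified, and SAP 6.3 does not impute neurological exam data. Naming the SAF as the population does not clearly override this.
- *Domains tested only in the full exam have no baseline.* SAP 4.5 supplies the Screening value.
- *The arm comparison is biased.* Both arms follow the same schedule, so at a given visit the misclassification favours neither. It adds background counts to both, which would pull a ratio toward 1.

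The importance is also limited. Peripheral sensory events needing a neurology consultation are a safety endpoint and an adverse event of special interest in their own right. The table is descriptive, dosing has stopped, and the full/brief schedule is printed in the same SAP.

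All of this stands. It does not answer the case of a domain tested in both versions: there the baseline rule selects the brief result over the full one, and nothing in SAP 5.9.10 tells the reader which visits are like with like.

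**Conclusion.** The point holds in a limited form. SAP 5.9.10 does not separate full from brief exams, and for domains tested on Day 1 the baseline rules set full-exam findings at Weeks 16 and 36 against a brief exam. Pre-existing abnormalities can be counted as new-onset, and rates may not be comparable across visits.

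This rests on the brief exam being less extensive within at least some domains. Its name implies that, but the documents do not spell it out. On the assumed ranges the excess is 0.3% to 5% of patients per domain, at most about one or two patients per arm, and it is zero if the brief exam is as sensitive as the full one. What is affected is the reading of the time course and the classification of individual findings, not the same-visit comparison between arms. It is a small correction, worth making because it concerns an identified risk and costs little.

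**What to change.** In SAP 5.9.10:

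- Judge new-onset at full-exam visits (Weeks 16 and 36, ET) against the full Screening exam, and at brief-exam visits (Weeks 2, 4, 8, 12 and 20) against the brief Day 1 exam. State this as an exception to the general baseline rule in SAP 4.5 and 6.1.
- Present full and brief visits in separate panels, or label each column with its exam version.
- Keep full ET exams out of windows whose scheduled exam is brief, and show them with the full exams.

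The cost is a few sentences and one table split, with no new data. Each series has fewer time points: five scheduled brief visits, and two scheduled full visits plus ET. The Screening exam is also older than the Day 1 exam, since the 7 to 10 day pre-randomization period lies between them. A footnote should therefore flag any patient already abnormal in that domain on Day 1.

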#### **5.9.11. Analysis of Pharmacokinetics and Drug Concentration Data**

Summaries of concentrations of functional fasinumab will be presented by nominal time point and dose. Plots of mean or median concentration of functional fasinumab will be presented by nominal day and dose.

#### **5.9.12. Analysis of Anti-Drug Antibody Data**

The ADA variables described in Section 4.7 will be summarized using descriptive statistics by dose/cohort group in the ADA analysis set. Prevalence of treatment-emergent and treatment-boosted ADA will be assessed as absolute occurrence (N) and percent of patients (%), grouped by study cohorts. For treatment emergent ADA, occurrence (N) and percent of patients (%) with persistent, transient and indeterminate ADA will be reported. The influence of treatment-emergent or treatment-boosted ADA assay response on individual PK profiles may be evaluated.

Listings of ADA positivity and titers presented by patient, time point, and dose cohort/group will also be provided.

Correlation analysis of safety versus treatment-emergent ADA positivity status may be performed on the SAF. Assessment will focus on the following safety events:

- Hypersensitivity (SMQ: Hypersensitivity [Narrow])
- Anaphylaxis (SMQ: Anaphylaxis[Narrow])

Number (%) of patients with the above-mentioned safety events may be summarized by treatment-emergent ADA positivity status, during the TEAE period.

In addition, correlation analysis of key efficacy endpoints versus treatment-emergent ADA status in patients who discontinued due to lack of efficacy may be summarized.

## 6. DATA CONVENTIONS

The following analysis conventions will be used in the statistical analysis.

For categorical variables, patients with missing data are not included in calculations of percentages unless otherwise specified. When relevant, the number of patients with missing data is presented.

### 6.1. Definition of Baseline for Variables

Unless otherwise specified, the baseline assessment for all efficacy measurements/ patient reported outcomes will be the latest available valid measurement prior to or on the day of randomization. Baseline for safety assessments such as labs, ECGs, vital signs etc. will be the latest assessment prior to the start of treatment.

### 6.2. Data Handling Conventions for Patient reported Outcomes data

#### ***LBPI NRS***

Baseline Average daily LBPI NRS score is defined as the average of the non-missing daily LBPI NRS scores for 7 days prior to randomization (from Day -6 to Day 1). Average daily LBPI NRS scores is calculated using the non-missing entries of the days as defined in the visit window mapping for electronic diaries in Section 6.4.

#### ***RMDQ***

The total score of the RMDQ is the total number of items checked by the patient (range of 0 to 24, with lower scores indicative of better function). The score can therefore vary from 0 to a maximum value of 24.

#### ***PGA LBP***

The PGA LBP is a patient assessed 5-point Likert scale of LBP (1=very well; 2=well; 3=fair; 4=poor; and 5=very poor).

#### ***BPI-sf***

The BPI-sf pain interference domain is a measure of how much pain has interfered with seven daily activities (items 9A-9G) including general activity, walking, normal work, mood, enjoyment of life, relations with others and sleep. The BPI-sf pain interference score is measured as the mean of the seven interference items.

#### ***WPAI-LBP***

WPAI outcomes are expressed as impairment percentages, with higher numbers indicating greater impairment and less productivity, i.e., worse outcomes as follows:

Questions:

1 = Currently employed?

2= hours missed due to LBP

3= hours missed due to other reasons

4= hours actually worked

5= degree LBP affected productivity while working

6= degree LBP affected regular activities

Scoring for the WPAI is as follows:

$$\text{Percent work time missed due to LBP} = Q2 / Q2 + Q4$$

$$\text{Percent impairment while working due to problem} = Q5 / 10$$

$$\text{Percent overall work impairment due to problem} = Q2 / (Q2 + Q4) + \left[ \left( 1 - \frac{Q2}{Q2 + Q4} \right) \times \left( \frac{Q5}{10} \right) \right]$$

$$\text{Percent activity impairment due to problem} = Q6 / 10$$

Multiply scores by 100 to express as a percentage

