##### **4.4.3. Exploratory Efficacy Variable(s)**

The exploratory efficacy endpoints to be assessed in the efficacy are:

- Change from baseline to week 16 in MOS Sleep-R Subscale Scores
- Change from baseline to week 16 in the 36-item Short Form Survey (SF-36) Subscale Scores
- Change from baseline to week 16 in the EuroQoL 5 Dimensions 5 Level Questionnaire (EQ-5D-5L) Scores
- Percentage of patients who used rescue medication
- Change from baseline to week 16 in Work Productivity and Activity Impairment-Low Back Pain (WPAI-LBP) questionnaire
  - percent of work time missed due to CLBP
  - percent of impairment while working due to CLBP
  - percent of overall work impairment due to CLBP
  - percent activity impairment due to CLBP
- Change from baseline to week 16 in the WOMAC pain subscale score

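### The SAP prints the WPAI-LBP formula for percent work time missed without parentheses, so read literally it returns 1 + Q4 instead of Q2/(Q2 + Q4)

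*SAP*

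**What the plan says.** SAP Section 4.4.3 lists four WPAI-LBP measures as exploratory efficacy variables, each analysed as change from baseline at week 16. One of them is "percent of work time missed due to CLBP".

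SAP Section 6.2 (WPAI-LBP) defines the items and the scoring. The relevant items are "2= hours missed due to LBP", "4= hours actually worked" and "5= degree LBP affected productivity while working". The scale is described thus: "WPAI outcomes are expressed as impairment percentages, with higher numbers indicating greater impairment and less productivity".

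The work-time score is printed as "Percent work time missed due to LBP} = Q2 / Q2 + Q4". (The stray brace comes from text conversion and plays no part in this point.) The overall score in the same list begins "Percent overall work impairment due to problem} = Q2 / (Q2 + Q4", closes the parenthesis, and adds one minus the same ratio, multiplied by Q5/10. The list ends with "Multiply scores by 100 to express as a percentage".

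The section gives no rule for a blank Q5, for Q4 = 0, for Q2 + Q4 = 0, or for a patient who is not employed. The same section does give missing-item rules for the SF-36, EQ-5D-5L, MOS-Sleep, WOMAC and TSQM. Protocol Section 8.2.2.11 gives no scoring and refers to the study reference manual for the questionnaire itself.

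**The concern.** These lines are the SAP's working specification for deriving the score, and two of them define the same ratio differently. A derivation that follows the first line literally gives values far above 100%. The score then rises with hours worked, ignores hours missed whenever any were missed, and cannot be computed for a patient who missed none.

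Because the measure is a change from baseline, the direction would be wrong as well as the size. A patient who returns to work more fully would be recorded as worse.

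**Working it through.** **Inputs.** Q2 is hours missed because of low back pain, Q4 is hours actually worked, and Q5 is the productivity rating, divided by 10 in the formula. All three definitions, the formulas and the factor of 100 come from SAP Section 6.2. The documents give no WPAI data or expected values, so there is no stated figure to reproduce. The hours below are illustrative assumptions.

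**Formulas for percent work time missed.**
- As printed, with standard operator precedence: (Q2/Q2) + Q4 = 1 + Q4 for Q2 > 0, and 0/0 at Q2 = 0.
- Grouped as in the overall-impairment line: Q2/(Q2 + Q4).

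| Q2 | Q4 | As printed, x 100 | Grouped, x 100 |
|---|---|---|---|
| 8 | 32 | (1 + 32) x 100 = 3300% | 8/40 = 20% |
| 4 | 36 | (1 + 36) x 100 = 3700% | 4/40 = 10% |
| 1 | 39 | (1 + 39) x 100 = 4000% | 1/40 = 2.5% |
| 0 | 40 | 0/0, undefined | 0/40 = 0% |
| 40 | 0 | (1 + 0) x 100 = 100% | 40/40 = 100% |

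Among these cases the two agree only when no hours were worked and some were missed.

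**Direction of change.** Take a patient who moves from 8 h missed and 32 h worked to 1 h missed and 39 h worked.
- Grouped: 2.5 - 20 = -17.5 points, an improvement.
- As printed: 4000 - 3300 = +700 points, a worsening.

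**Overall work impairment, as printed.** The formula is Q2/(Q2 + Q4) + [1 - Q2/(Q2 + Q4)] x Q5/10.
- Q2 = 8, Q4 = 32, Q5 = 5: 0.20 + 0.80 x 0.5 = 0.60, or 60%. This is a sensible value on the stated scale.
- Q2 = 40, Q4 = 0, Q5 = 0, 5 or 10: 1 + 0 x Q5/10 = 1, or 100% each time.
- Q2 = 40, Q4 = 0, Q5 blank: the algebra still fixes the answer at 100%. Software that propagates missing values, as SAS arithmetic operators do (SAP Section 9 names SAS), returns missing.
- Q2 = Q4 = 0: 0/0, so both this score and the corrected work-time score are undefined.

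**The case against.** The strongest reply is that this is a misprint that its own context resolves. The overall-impairment line shows the intended ratio, the introductory sentence fixes the scale, and a value such as 3300% would be noticed at once. That is largely right about intent, and a careful programmer would probably not follow the line literally. It does not make the line correct. The SAP exists to fix derivations before lock, and two of its lines disagree.

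A second reply is that parentheses or a fraction bar may have been lost in conversion from PDF. This cannot be excluded, but it is unlikely: both inline parentheses and stacked fractions survive in the overall-impairment formula of the same list.

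A third reply is that little depends on it. That stands, and it limits the weight of the point.

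A reader might go further and infer that overall work impairment is also mis-scored, that patients with complete work absence drop out of its mean, and that the arm with more absence therefore looks better. The documents do not support this. That formula is correctly grouped and returns 100% for a patient with Q4 = 0 and Q2 > 0 who answers Q5. It goes missing there only if Q5 is blank. The item wording makes a blank answer plausible when no hours were worked, but neither document says that Q5 is skipped, and the questionnaire is not available here. A bias between arms would also need such patients to be unevenly split, and the documents give no counts of employed or fully absent patients. What remains is missing detail about an edge case.

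**Conclusion.** The printed work-time formula is wrong as written. It gives 1 + Q4 for Q2 > 0 and is undefined at Q2 = 0, in conflict with the correctly grouped ratio in the same list and with the stated percentage scale. Whether any result is affected depends on the line being programmed literally.

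The reach is small. One of four WPAI measures is involved; it is exploratory (SAP Section 4.4.3). SAP Section 5.8 drops formal testing and keeps efficacy descriptive, and SAP Section 1.1 reports that 63 patients had been randomized when dosing stopped. No primary, secondary or safety endpoint is affected. The overall-impairment formula needs no correction. The lack of a rule for blank Q5 or zero hours is a clarification, and its practical effect rests on an assumption that the documents do not state.

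**What to change.** Print the formula as percent work time missed = Q2/(Q2 + Q4) x 100.

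As an optional clarification, add two rules:
- If Q2 > 0 and Q4 = 0, overall work impairment is 100%, even if Q5 is blank.
- If the patient is not employed, or Q2 + Q4 = 0, the three work scores are missing and only activity impairment is scored.

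The cost is one corrected line and, if wanted, two sentences. No new data are needed, and SAP Section 1 allows blinded revision before database lock. If programming has already begun, check the derivation code against the grouped ratio.
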